1.2 Secondary Objectives

1.2.1 Delayed and Sustained Effects

We will use binary regression models with random intercepts fit by maximum likelihood to examine whether the proportion of community ambulators differs between the PUSH and PULSE interventions at 40 weeks post-randomization. Also we will assess whether the difference in proportions at 40 weeks changed from the difference in proportions at 16 weeks. This approach will implicitly take into consideration the 16-week outcome in estimating the 40-week outcome and thereby provides some protection against biases due to missing data. The longitudinal model for this aim is expressed by the equation:

$$p_{ij} = a_i + b_1 X_i + b_2 t_{40_{ij}} + b_3 X_i t_{40_{ij}}. \quad (\text{Eq. 1})$$

where p_{ij} is the probability of a community ambulation for participant i at time j , a_i is the random intercept for participant i , X_i is the intervention indicator (1/0) variable; b_1 is the treatment effect at 16 weeks; $t_{40_{ij}}$ is the 40-week follow-up time post-randomization indicator (0=16 weeks; 1=40 weeks); and $X_i t_{40_{ij}}$ is the intervention-by-time interaction variable. In fitting this model, 16-week data points with indeterminate outcomes will not be included. Also 40-week data points with indeterminate or missing (by design) outcomes will not be included. The fitted coefficients in Eq. 1 provide estimates of the proportion of community ambulators in the PUSH vs PULSE interventions at 16 and 40 weeks post-randomization. To test the null hypothesis of equal

proportion of community ambulators in both groups at 40 weeks post-randomization, we will test the null hypothesis $H_0: (b_1+b_3)=0$ using a two-sided test with type I error of 0.05. This test will be performed regardless of results from the primary aim. However, the interpretation of results from this test will depend on those from the primary aim. If there is evidence for a difference in proportion of community ambulators at 16 weeks, then rejecting this hypothesis can be interpreted as evidence for a sustained effect of the PUSH intervention on community ambulation at 40 weeks; if there is no evidence for a difference in proportion of community ambulators at 16 weeks, then rejecting this hypothesis can be interpreted as evidence for a delayed effect of the PUSH intervention on community ambulation at 40 weeks. We are also interested in describing the trends in community ambulation from 16 to 40 weeks post-randomization in both groups. To assess the null hypothesis of no change in the between-group difference of proportion of community ambulators between 16 and 40 weeks post-randomization, we will test the null hypothesis $H_0: b_3=0$ using a Wald chi-square test with type I error of 0.05. All treatment effects will be reported with their respective 95% confidence intervals.

To estimate delayed response and sustainability at an individual level, we will analyze the 40-week community ambulation results in strata defined by the 16-week results. Among those who were not community ambulators at 16 weeks, we will determine the proportion who were community ambulators at 40 weeks. Similarly, of those who were community ambulators at 16 weeks, we will estimate the proportion who were community ambulators at 40 weeks. This information can be summarized in each treatment group using a 3 by 3 table with rows and columns indicating community ambulation at 16 and 40 weeks, respectively (yes, no, indeterminate).

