4.2 Secondary Objectives

Delayed and sustained effects. A secondary objective will be to determine whether the proportion of community ambulators differs between the PUSH and PULSE interventions at 40 weeks post-randomization and, for the subset of participants who were followed for 40 weeks, whether the difference in proportions at 40 weeks changed from the difference in proportions at 16 weeks.

Effect on secondary and tertiary outcomes. There are five variables (endurance, dynamic balance, walking speed, quadriceps strength, and lower extremity function) that are hypothesized to be precursors to community ambulation. To gain a better understanding of the interventions' mechanisms, the two groups will be compared at 16 weeks post-randomization on each of these outcomes and at 40 weeks post-randomization for the subset of participants who are followed for 40 weeks. In addition, this study will assess the effect of the interventions on several tertiary outcomes including ADLs, balance confidence, quality of life, physical activity, lower extremity physical performance, depressive symptoms, increase of ≥ 50 meters in distance walked in six minutes, cognitive status, and nutritional status.

Cost-effectiveness of the interventions. The economic value of the interventions will be determined by assessing the impact on QALYs, cost, and cost per QALY gained over the follow-up period. This RCT will provide critical information on whether the specific PUSH intervention can improve a hip fracture patient's ability to ambulate in the community in a cost-effective manner compared to the non-specific PULSE intervention. To address the economic value of trial interventions versus usual care, a model-based analysis that combines trial data with other data sources also will be undertaken.

Section 5: Background

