where p is the probability of a particular outcome, $\text{Logit}(p) = \ln(p/(1-p))$, X is the intervention indicator (1/0) variable; b_1 is the treatment effect at 16 weeks; t_{40} is the 40-week follow-up time post-randomization indicator (0=16 weeks; 1=40 weeks); and $X t_{40}$ is the intervention-by-time interaction variable. The fitted coefficients in Eq.1 provide estimates of the proportion of community ambulators in the PUSH vs PULSE interventions at 16 and 40 weeks post-randomization. To test the null hypothesis of equal proportion of community ambulators in both groups at 40 weeks post-randomization, we will test the null hypothesis $H_0: (b_1+b_3)=0$ using a two-sided test with type I error of 0.05. This test will be performed regardless of results from the primary aim. However, the interpretation of results from this test will depend on those from the primary aim. If there is evidence for a difference in proportion of community ambulators at 16 weeks, then rejecting this hypothesis can be interpreted as evidence for a sustained effect of the PUSH intervention on community ambulation at 40 weeks; if there is no evidence for a difference in proportion of community ambulators at 16 weeks, then rejecting this hypothesis can be interpreted as evidence for a delayed effect of the PUSH intervention on community ambulation at 40 weeks. We are also interested in describing the trends in community ambulation from 16 to 40 weeks post-randomization in both groups. To assess the null hypothesis of no change in the between-group difference of proportion of community ambulators between 16 and 40 weeks post-randomization, we will test the null hypothesis $H_0: b_3=0$ using a Wald chi-square test with type I error of 0.05. All treatment effects will be reported with their respective 95% confidence intervals.

A similar approach will be used to examine delayed and sustained effects for the secondary and

tertiary outcomes described below.

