1.1.3 Assessment of effect modification by site, period, and patient characteristics

Study site will be investigated as a modifier of the effect of the intervention by testing a site-by-intervention interaction term on the risk difference scale based on a binary regression model

with an identity link. If there is evidence that study site is an effect modifier (i.e., $p < 0.1$ for the interaction term), we will report site-specific treatment effects.

In the fall of 2014, a decision was made to modify the frequency of intervention visits during the first 8 weeks from 3 per week to 2 per week. We will assess the impact of this protocol change on the intervention outcomes in a secondary analysis. To do so, assuming no significant interaction between site and intervention group, we will assess the statistical significance of the interaction between the period during which the participant was randomized (before vs after the protocol change) and treatment group. If there is a significant interaction, then we will make separate treatment group comparisons in the two periods (one comparison for participants randomized during the period when there were three sessions per week and another for participants randomized during the period when there were two sessions per week).

In addition, a series of analyses will be performed to examine the differential impact of the PUSH intervention relative to the PULSE intervention in subgroups defined by participant characteristics. To do this, a variable-by-intervention interaction term will be tested for each of the following variables:

1. Gender
2. Age at baseline (≥ 85 years versus 60-84 years)
3. Baseline depression (CES-D score ≥ 16 versus CES-D score < 16)
4. Baseline balance confidence (with median Activities-Specific Balance Confidence scale score as the cutpoint to define the subgroups)
5. Baseline nutritional status (MNA®-SF score < 8 versus MNA®-SF score ≥ 8)
6. Baseline cognitive status (3MS score < 91 versus 3MS score ≥ 91)
7. Baseline physical performance (SPPB score < 7 versus SPPB score ≥ 7)

If the interaction term for any of these subgroup variables is significant, results will be presented separately in strata of the subgroup variable.

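### SAP 1.2.1 lets a significant week-40 test after a missed week-16 primary test be read as a delayed effect, without tying that reading to the planned test of change (b3)

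*SAP*

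**What the plan says.** SAP 1.2.1 models the probability of community ambulation at weeks 16 and 40 with an identity link and a random intercept (Eq. 1). There b1 is the treatment difference at week 16, b3 is the change in that difference by week 40, and b1+b3 is the difference at week 40.

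The section tests b1+b3=0 with a two-sided 0.05 test, whatever the primary result, and adds that "the interpretation of results from this test will depend on those from the primary aim". Evidence of a difference at week 16 makes a week-40 rejection a sustained effect. Without such evidence, "then rejecting this hypothesis can be interpreted as evidence for a delayed effect of the PUSH intervention on community ambulation at 40 weeks". The clause does not mention b3. Protocol 15.2.1 has a matching sentence for its own model: "if there is no evidence for a difference in proportion of community ambulators at 16 weeks, then rejecting this hypothesis can be interpreted as evidence" of a delayed effect.

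The same SAP section also plans to examine the change directly. It states "Also we will assess whether the difference in proportions at 40 weeks changed from the difference in proportions at 16 weeks", and for this "we will test the null hypothesis $H_0: b_3=0$ using a Wald chi-square test with type I error of 0.05". The b3 test is introduced as a description of trends. The section also promises 95% confidence intervals for all treatment effects and a table of 16-week by 40-week status in each arm: "To estimate delayed response and sustainability at an individual level, we will analyze the 40-week community ambulation results in strata".

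**The concern.** To call an effect delayed is to say that it was absent or smaller at week 16 and emerged or grew afterwards. That is a statement about b3. The clause draws it instead from the contrast between a test that missed and a test that succeeded, and this contrast can arise when the true difference is the same at both visits.

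The two tests also differ in form and sample. Week 16 is a one-sided 0.025 group sequential procedure with final boundary Z = 2.03, planned on 210 participants less 6.8%. Week 40 is a two-sided 0.05 test on about 150 participants less 10% indeterminate.

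What is at stake is the worded conclusion. The clause operates when the primary test has missed, which is when a statement about a delayed effect would carry most weight in the report. As written, that statement is permitted even if the b3 estimate reported beside it is close to zero.

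**Working it through.** **Inputs from the documents.** PULSE 16%, PUSH 36%, 105 per arm, 6.8% loss, 12.2% non-compliance (protocol 15.6.1). About 150 participants with week-40 data, 10% of them indeterminate, stated power 64% (protocol 15.6.2). Final boundary 2.03 (SAP 1.1.1, Table 1).

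**Derived quantities.**
- Week 16: 105 × (1 − 0.068) = 97.9, taken as 98 per arm.
- Week 40: 150 × 0.90 / 2 = 67.5, taken as 67 per arm.
- Diluted effect: 0.20 × (1 − 0.122) = 0.1756, so PUSH = 0.16 + 0.1756 = 0.3356.

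**The plan's own figure.** Power = Φ[(d − 1.96·SE0)/SE1], with d = 0.1756, 67.5 per arm and mean rate 0.2478.
- SE0 = √(2 × 0.2478 × 0.7522 / 67.5) = 0.0743
- SE1 = √((0.16 × 0.84 + 0.3356 × 0.6644) / 67.5) = 0.0728
- Power = Φ[(0.1756 − 0.1457)/0.0728] = Φ(0.41) = 66%, within 2 points of the stated 64%.

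The inputs are therefore close to those the plan used.

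**A single example.**
- Week 16: 27/98 vs 16/98. Difference 11.2 points, pooled rate 43/196, SE 0.0591, Z = 1.90, below 2.03.
- Week 40: 21/67 vs 11/67. Difference 14.9 points, pooled rate 32/134, SE 0.0737, Z = 2.03, above 1.96.

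The clause permits the delayed reading, yet the difference moved by only 14.9 − 11.2 = 3.7 points. If the week-40 completers share the week-16 rates and the yes/no correlation is 0.5, the z-value for b3 is about 0.5.

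**How often this happens with no change.** Simulation of 40,000 trials per setting: PULSE 16% and a 17.6-point difference at both visits, with the label given when Z ≤ 2.03 at week 16 and Z > 1.96 at week 40. The correlation between visits is not in the documents. It was set at 0.70 and 0.85, applied either to an underlying (latent) walking distance or to the yes/no outcome itself. A latent correlation of 0.70–0.85 corresponds to about 0.44–0.64 on the yes/no scale. The SAP's random-intercept model was not fitted. Two stand-ins were used: simple Z-tests (b3 from paired change in completers), and a likelihood estimate that also uses all week-16 data.

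| Correlation applied to | Analysis | r = 0.70 | r = 0.85 |
|---|---|---|---|
| Latent distance | Simple Z-tests | 9.0% | 7.2% |
| Latent distance | All week-16 data | 9.8% | 8.5% |
| Yes/no outcome | Simple Z-tests | 6.4% | 4.5% |
| Yes/no outcome | All week-16 data | 7.7% | 6.2% |

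Adding the four planned efficacy looks changes these little (3.9% to 9.5%). In 84–88% of the labelled trials b3 is not significantly above 0. The primary test misses in about 20% of these trials, and between 23% and 49% of those that miss would then meet the delayed wording.

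**When the effect shrinks.** With a true difference falling from 15 to 12 points (latent correlation, simple Z-tests), 7.5% (r = 0.70) and 5.5% (r = 0.85) of trials still meet the wording.

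**The case against.** The strongest reply is that the plan already supplies the evidence needed. The b3 test is in the same section, with confidence intervals and the tables by 16-week status, and the clause is permissive rather than mandatory. Most of this stands. It is why the matter is minor: in most wrongly labelled trials a reader would see a non-significant b3 beside the label. It does not remove the point, because no b3 result can withhold the label, and a pre-specified permission is what a report would cite.

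Four stronger readings are tempting, and the documents do not support them.

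- *That the secondary objective is left unanswered.* Protocol 4.2 asks whether the groups differ at week 40 and, separately, "whether the difference in proportions at 40 weeks changed from the difference in proportions at 16 weeks". The second question is answered directly by the b3 test. The disputed clause only interprets the first.
- *That no evidence at week 16 is undefined.* The SAP ties interpretation to the primary aim, which has explicit decision boundaries. The p < 0.1 in SAP 1.1.3 ("If there is evidence that study site is an effect modifier") is defined there for the site interaction and does not carry over.
- *That protocol 15.2.1 needs the same b3 condition.* Protocol Eq. 1 is a logit model, so its b3 is a change in log odds ratio. If, for illustration, PULSE rose from 16% to 30%, a constant 17.6-point difference would give a logit b3 of −0.23. The SAP changed the scale so that estimates read as rate differences, and says that it departs from the protocol's plan.
- *That the label should be barred unless the b3 interval excludes 0.* b3 has limited power. For a true rise from 8 to 20 points (latent correlation, simple Z-tests), such a gate would cut correct labels from about 52–53% to 29–34%. That is a trade-off, not a correction the documents require.

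**Conclusion.** The point holds as a matter of interpretation. The clause infers a change over time from one missed and one significant test, and does not refer to the parameter that measures the change. Under a constant 17.6-point effect, about 4–10% of trials would meet the delayed wording, and in about 85% of these b3 would not be significantly above 0. Those figures depend on the assumed constant effect, the 16% PULSE rate at both visits, the assumed correlation of 0.70–0.85, and the stand-ins for the random-intercept model. That the pattern does not by itself show growth does not depend on them. The week-40 test remains a valid test of a 40-week effect, and no test, estimate or primary conclusion is affected. Severity is minor.

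**What to change.** In SAP 1.2.1 only, keep the sustained-effect clause and replace the delayed-effect clause with wording such as: 'If the primary test does not show a difference at 16 weeks, rejecting this hypothesis is evidence of an effect at 40 weeks. Whether the effect is delayed will be judged from b3 and its 95% CI, reported alongside; where these do not support an increase from week 16, the result will be described as a 40-week effect without clear evidence that it differs from week 16.'

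The cost is one clause and no new analysis, since b3 and its interval are already planned. The downside is that, because b3 has limited power, some truly delayed effects would be described more cautiously. The 40-week effect and b3 with its interval would still be reported in every case.

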1.2.2 Secondary and Tertiary Outcomes

Secondary outcomes include five variables (endurance, dynamic balance, walking speed, quadriceps strength, and lower extremity function) that are hypothesized to be precursors to community ambulation. In addition, we will examine the difference between the treatments with respect to the following tertiary outcomes: ADLs, balance confidence, quality of life, physical activity, lower extremity physical performance, depressive symptoms, increase of ≥ 50 meters in distance walked in six minutes, cognitive status, and nutritional status.

With the exception of “increase of 50 meters in distance walked in six minutes”, these variables are quantitative. Prior to analyzing the relationship between treatment and the quantitative variables we will use histograms and side-by-side box plots to examine the shape of the distributions and identify potential outliers. If the data strongly depart from normality, we will consider transforming the data or using rank-based methods for the analyses described below.

Mixed effects models fit by restricted maximum likelihood will be used to compare the PUSH and PULSE interventions at 16 and 40 weeks post-randomization with respect to each outcome. Increase of ≥ 50 m in distance walked, a dichotomous outcome, will be analyzed using the same method as the primary outcome. All of the other secondary and tertiary outcomes are continuous; therefore, a normal model will be used to estimate the parameters in the following equation:

$$\mu_{ij} = b_0 + b_1 t_{16_{ij}} + b_2 t_{40_{ij}} + b_3 X_i t_{16_{ij}} + b_4 X_i t_{40_{ij}}, \quad (\text{Eq. 2})$$

where μ_{ij} is the mean of the j th outcome from the i th participant, X_i is the intervention indicator (1/0) variable; $t_{16_{ij}}$ and $t_{40_{ij}}$ are the 16- and 40-week follow-up time post-randomization indicators, respectively; and $X_i t_{16_{ij}}$ and $X_i t_{40_{ij}}$ are the intervention-by-time interaction variables.

To account for the correlation between repeated measures from the same person, we will fit an unstructured variance/covariance matrix to the three time points. This model accounts for outcomes at three time points: baseline, 16 weeks, and 40 weeks post-randomization. By treating the baseline value as an outcome, we quantify mean changes in the outcome relative to baseline levels. Differences between the two groups in changes from baseline to 16 and 40 weeks post-randomization will be compared using Eq. 2 by testing $H_0: b_3=0$ and $H_0: b_4=0$ respectively using a Wald chi-square test with type-I error of 0.05. All treatment effects will be reported with their respective 95% confidence intervals.

1.3 Cost-Effectiveness of Interventions

To assess the cost-effectiveness of study interventions, the EEC will conduct analyses of within-trial comparisons for the economic endpoints (resource utilization/costs and SF-6D/QALYs) and will also undertake a model-based analysis that allows the economic value of both study interventions to be assessed relative to usual care. Longitudinal modeling appropriate for repeated measures data will be used to make inferences on the overall differences in cost and QALYs associated with the study interventions. The basic statistical analyses of cost and QALYs will be similar to the approach described for other study endpoints, but will be undertaken in the EEC in close collaboration with the DCC.

Statistical analyses of SF-6D will produce an estimate of the incremental QALYs associated with the PUSH intervention at each time point where SF-36 is measured. The estimated difference in QALYs attributable to the PUSH intervention will be estimated by taking a time-weighted average of the time-specific intervention effects. Statistical analyses of cost data, which will be adjusted to a constant dollar year (e.g., 2012 US dollars), will produce an estimate of the incremental costs associated with the PUSH vs. PULSE intervention.

The incremental cost-effectiveness ratio (ICER), which is defined as the net change in cost divided by the net change in effectiveness (QALYs) when interventions are ranked in order of increasing cost, is the focus of the economic analysis. When estimated as added cost per QALY gained, the ICER allows the value of interventions in hip fracture to be compared with interventions in other diseases. ICERs will be estimated using both the statistical analysis of cost and QALY data (i.e., trial-based ICER) and a model-based analysis that combines trial results with other existing data (i.e., model-based ICER). The trial-based ICER addresses the economic value of the PUSH intervention relative to the PULSE, while the model-based ICER estimates the economic value of the study interventions relative to usual care (as described below).

The second objective of the cost-effectiveness analysis is to develop and implement a decision-analytic modeling framework that will incorporate within-trial findings regarding costs and QALYs for the purpose of evaluating the cost-effectiveness of the PUSH intervention and PULSE relative to usual care. Model-based analyses are commonly employed to extend or augment clinical trials because the cost of trials precludes study of all interventions of interest and because it is often desirable to consider the value of interventions over a longer time horizon than what is observed in the trial. To make inferences about the economic value of the study interventions relative to usual care, a Markov state-transition modeling framework that incorporates trial results will be developed and utilized. Estimates of the cost of the study interventions will be derived from time estimates recorded in the field over the course of the study. Estimates of the QALY impact of usual care will be derived from existing hip fracture cohorts (control arms of other trials). Estimates of changes in SF-6D for similar patient groups are available from the control arms of BHS RCTs. Because these studies have tracked resource utilization with few questions and follow up measures, extensive sensitivity analyses that vary

the impact of the interventions on resource utilization will be undertaken to characterize the magnitude of change in costs that would be required to qualitatively affect the conclusions of the economic analysis.

The model-based ICER for the study interventions relative to usual care will be compared qualitatively with the costs per additional QALY estimates of other commonly accepted medical interventions. Uncertainty in the model-based analysis will include estimation of cost-effectiveness acceptability curves, which represent the probability that a particular cost-effectiveness threshold (e.g., \$100,000 per QALY gained) is achieved when variability in cost and QALYs is considered in probabilistic sensitivity analyses.

The above cost-effectiveness analyses will not be performed unless at least one of the two following conditions is satisfied:

- There is a statistically significant difference in the primary outcome between groups, OR
- There is a statistically significant and clinically meaningful between group difference in any of the secondary outcomes listed below.

Clinically meaningful differences for the secondary outcomes at 16 and 40-week follow-up:

	Clinically Meaningful Difference
Other Secondary Outcomes:	
Distance walked in 6 minutes (m)	50 m ¹
Short Physical Performance Battery score	1.0 ¹
Gait speed, 50-ft fast walk (m/s)	0.10 m/s ²
Gait speed, 4-m usual walk (m/s)	0.10m/s ¹

¹Perara et al, 2006

²Palombaro et al, 2006

